#### 4.0 LIST OF ABBREVIATIONS AND DEFINITION OF TERMS

Abbreviation or Term	Definition/Explanation
AChEI	Acetylcholinesterase inhibitor
AD	Alzheimer's disease
ADAS-Cog	Alzheimer's Disease (AD) Assessment Scale-Cognitive Subscale
AE	Adverse Event
Ae	Amount excreted
ALT (SGPT)	Alanine aminotransferase (Serum Glutamic Pyruvic Transaminase)
ALP	Alkaline phosphatase
ANOVA	Analysis of Variance
AST (SGOT)	Aspartate aminotransferase (Serum Glutamic Oxaloacetic Transaminase)
ATC	Anatomical Therapeutic Chemical Classification
AUC	Area Under the Curve
AUC 0-∞	Area under the curve from time zero to infinity
AUC 0-t	Area under the curve from time zero to last concentration above LOQ
BID	Bis in die, twice a day dosing (or QD [once daily])
BLQ	Below Limit of Quantification
BMI	Body mass index
BUN	Blood Urea Nitrogen
C	Celsius
CDR	Clinical Dementia Rating: numeric scale used to quantify the severity of symptoms of dementia
C max	Maximum concentration
CRF	Case Report Form
CNS	Central nervous system
C-SSRS	Columbia-Suicide Severity Rating Scale
CT	Computed tomography
dL	Deciliter
DSM-5	Diagnostic and Statistical Manual of Mental Disorders, 5th Edition
EC	Ethics Committee
ECG	Electrocardiogram
eCRF	Electronic Case Report Form
ERP	Event related potential

Abbreviation or Term	Definition/Explanation
EudraCT	European Union Drug Regulating Authorities Clinical Trials is the European Clinical Trials Database of all clinical trials of investigational medicinal products
FDA	Food and Drug Administration
Fe	Fraction (%) of amount excreted
FSH	Follicle stimulating hormone
g	Gram
GFR	Glomerular Filtration Rate
GlcNAc	$\beta$ -D-N-acetylglucosamine
Hct	Hematocrit
Hgb	Hemoglobin
HIV	Human immunodeficiency virus
IB	Investigator Brochure
HIPAA	Health Information Portability and Accountability Act of 1996
ICH	International Conference on Harmonization
IEC	Institutional ethics committee
IMP	Investigational Medical Product
IND	Investigational New Drug
INR	International Normalized Ratio
IRB	Institutional Review Board
IU	International unit
IV	Intravenous
IWRS	Interactive Web Response System,
kg	Kilogram
L	Liter
LLOQ	Lower limit of quantification
$\lambda_Z$	Rate elimination constant
$\mu g$	Microgram
MAD	Multiple ascending dose
MedDRA	Medical Dictionary for Regulatory Activities
mg	Milligram
mL	Milliliter
mmHg	Millimeters of Mercury

Abbreviation or Term	Definition/Explanation
MMSE	Mini-Mental State Examination
MOA	Mode of action
MRI	Magnetic resonance imaging
NCI CTCAE	National Cancer Institute-Common Terminology Criteria for Adverse Events
N	Normal
ng	Nanogram
NFTs	Neurofibrillary tangles
NOAEL	Non observable adverse effect level
OGA	O-linked- $\beta$ -N-acetylglucosaminidase
O-GlcNAcase	O-linked-N-acetylglucosaminyltransferase or OGA
OGT	O-linked-N-acetylglucosaminyltransferase
PBMC	Peripheral blood mononuclear cell
PD	Parkinson's disease
PET	Positron emission tomography
pH	Hydrogen ion concentration
PHF	Paired helical filament
PR	ECG: time from the beginning of the P wave to the beginning of the QRS complex
Pre	Before
QD	Quaque die, once daily
QRS	ECG: The QRS complex represents the electrical impulse as it spreads through the heart ventricles
PSP	Progressive Supranuclear Palsy
PT	Preferred Term
QT	measurement that represents the total time interval from ventricular depolarization to complete repolarization
QTcB	heart rate-corrected QT interval according to Bazett's formula
QTcF	heart rate-corrected QT interval according to Fridericia's formula
RBC	Red Blood Cell
ROI	Region of interest
SAD	Single ascending dose
SAE	Serious Adverse Event
SAP	Statistical Analysis Plan
SC	Subcutaneous

Abbreviation or Term	Definition/Explanation
SD	Standard Deviation
SF	Straight filament
SGOT (AST)	Serum Glutamic Oxaloacetic Transaminase
SGPT (ALT)	Serum Glutamic Pyruvic Transaminase
SOC	System Organ Class
SRC	Safety Review Committee
$t_{1/2}$	Terminal elimination phase half-life
TEAE	Treatment-emergent adverse event
$t_{max}$	Time to maximum concentration
ULN	Upper limit of normal
ULOQ	Upper limit of quantification
US	United States
WBC	White Blood Cell
$V_{ND}$	Non-displaceable volume of distribution
$V_T$	Regional total volume of distribution

## 5.0 INTRODUCTION AND RATIONALE

ASN51 [REDACTED]

[REDACTED] is under development for the treatment of neurodegenerative diseases caused by intracellular protein aggregates (proteinopathies) in the brain. ASN51 is indicated for the treatment of adults with Alzheimer's Disease (AD).

[REDACTED]

[REDACTED]

[REDACTED]

[figure not shown]
[REDACTED]

This single dose open study is a human Phase 1 trial in healthy adult (HA) subjects investigating the target receptor brain occupancy of ASN51 by means of PET scans. Establishing the target brain occupancy is important for dose selection because it has been shown [REDACTED]

[figure not shown]
[REDACTED]

[figure not shown]
[REDACTED] These data will serve as a basis for the dosing and dosing regimen in further clinical studies. The safety of ASN51 has been evaluated and there were no findings in non-clinical studies to date which would preclude the initiation of the planned Phase 1 study.

[figure not shown]
**5.1 Background: O-GlcNAcylation and Protein Aggregation in Neurodegenerative Disease**

## 5.2 ASN51 Mechanism of Action and Rationale in Alzheimer's Disease

[figure not shown]

[figure not shown]

[figure not shown]

### **5.3 Nonclinical Studies**

Nonclinical findings of potential clinical significance and relevance to this protocol are summarized briefly below; additional information is provided in the IB.

[figure not shown]

[figure not shown]

#### **5.4 Clinical Experience**

This study will be conducted in parallel to a separate Phase 1 single ascending dose (SAD) tolerability study in healthy young adult subjects (ASN51-101). Safety and pharmacokinetic data for each SAD cohort will be determined in ASN51-101 and will be reviewed by the safety review committee (SRC) prior to dosing in ASN51-102 at each respective dose level ([Section 7.5.1](#)). Safety, pharmacokinetic and pharmacodynamic PET data will be assessed by the SRC prior to any further dosing in this study to determine the next dose level to be administered as well as the timing of the next PET scan in relation to the time of the study drug administration. Any dose level set by the SRC will not exceed 85% of the highest well-tolerated dose level in the single rising dose tolerability study ASN51-101.

#### **5.5 Summary of Overall Risks and Potential Benefits**

Risks attributable to the COVID-19 pandemic: To address these specific risks, a risk mitigation plan for staff, volunteers, and visitors will be followed throughout the study see also [Section 13.4](#).

## 6.0 OBJECTIVES

### Primary Objective

- To assess the brain O-GlcNAcase occupancy using [F] IMA601 PET, following a single oral dose of ASN51

## Secondary Objectives

- To assess the relationship between the plasma concentration of ASN51, and the time-course of brain O-GlcNAcase occupancy using [F]-IMA601 PET, following a single oral dose of ASN51
- To assess the single dose safety and tolerability of ASN51 in healthy adult subjects under fasted conditions

## 7.0 INVESTIGATIONAL PLAN

### 7.1 Study Design

This is an open-label, adaptive-design PET study to investigate the occupancy of O-GlcNAcase by ASN51 after single oral doses in healthy adult male and female subjects (aged 25-55 years, inclusive). The study schema is depicted in [Figure 2](#).

**Figure 2:** Phase 1a ASN51-102 Study Schema

Up to 10 subjects will be enrolled. Each subject will have up to 3 imaging sessions, with one scan in each session. In the first imaging session, subjects will have 240 ml of water followed by a baseline PET scan approximately 2 h later. In the second and third imaging sessions, subjects will receive a single oral dose of ASN51 with 240 ml of water, followed by an on-treatment PET scan. Safety and pharmacokinetic data of the SAD study ASN51-101 will be assessed by the SRC prior to the dosing of the first subject(s) to determine the first dose level to be administered in session 2 after the baseline session 1 and the timing of the PET scans in relation to the study drug administration time. At most 2 subjects will be dosed on the same study day. For subsequent sessions, the dose level and the time of the PET scan in all imaging session 2 and 3 will be determined after review of the results from the first on-treatment PET scan, including the PK data. Subjects will receive an intravenous dose of the radiolabelled tracer, [F]-IMA601, at the start of each PET scan.

This study will have an adaptive design: to adequately evaluate the exposure versus receptor occupancy (RO) relationship, various doses of ASN51 of up to 85% of the highest well-tolerated dose level in the preceding SAD study ASN51-101, and the timing of on-treatment PET scans may

be altered based on emerging data or study logistical requirements. On-treatment PET scans may be scheduled up to 48 h post-dose.

After each on-treatment PET scan, the SRC will review available RO, PK, safety and tolerability data, before selecting the dose and PET scan timings for imaging session 3. Arterial blood sampling will be done during each PET scan to quantify the parent tracer related radioactivity over the course of the PET scan, and to establish a tracer metabolite corrected plasma input function. The total arterial blood volume required for each tracer injection will not exceed 145 mL. Arterial cannulation and arterial blood sampling may be reduced or removed if analysis of PET data from previous subjects indicates that noninvasive analysis of the PET scan data can be done. If a non-invasive analysis is not possible, the use of an arterial cannula with each PET scan will continue through the study.

Subjects will be screened within 21 days before their baseline PET scan. Their on-treatment PET scans will be within 7 days of their baseline scan with an interval of 7–14 days between imaging sessions 2 and 3. Subjects will be confined for 72 h after the study drug administration in sessions 2 and 3. After the baseline scan in session 1 without study drug administration, subjects may leave the unit in the evening. In the case of a technical failure (such as unsuccessful tracer synthesis), subjects may be asked to attend an additional on-treatment imaging session, in which they will receive a third oral dose of ASN51. There will be at least 7 days between each dose of ASN51. Subjects will not have more than 3 PET scans or 3 doses of ASN51 during the study. Subjects will have a follow-up visit at the research unit 7 days ( $\pm$  3 days) after imaging session 3 (Day 8).

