- Screening Assessments:** Screening will be within 21 days before imaging session 1.
- Imaging Admissions:** Admission for imaging session 2 will be within 7 days after the baseline PET scan; and admission for imaging session 3 will be within 7–14 days after imaging session 2.
- PET Repeat/Reschedule:** In the case of technical failures (i.e., such as unsuccessful tracer synthesis or a PET scanner malfunction etc.) a PET scan may need to be repeated or rescheduled. In such cases, subjects may be asked to stay for up to 48 h longer in each imaging session or repeat an imaging session at a later date. If the failure affects imaging session 1 before administration of radioactivity, the baseline scan may be repeated. If the failure affects imaging session 1 after administration of radioactivity, the baseline scan may be repeated once. If the technical failure affects imaging sessions 2 or 3 (after the subject has received an ASN51 dose), a third imaging session may be required, after a 7-day washout of the last dose of ASN51. Subjects will receive no more than 3 single doses of ASN51, or 3 doses of [F]-IMA601 during the study.
- Follow-up Visit or ET:** A follow up visit will be 7 days ( $\pm 3$  days) after the last on-treatment PET scan. Additional follow-up by telephone for any potential SAEs will be 28 days ( $\pm 3$  days) after the last on-treatment PET scan.
- Inpatient Stay:** Subjects will be admitted on Day -1 of imaging sessions 1, 2 and 3. Subjects will remain inpatient for both imaging sessions 2 and 3 for up to 72 h after dosing. In session 1, subject may leave the clinical unit in the evening of Day 1.
- MRI Questionnaire:** Subjects will complete an MRI questionnaire before the MRI scan, to exclude unsuitable subjects.

7. **MRI Scan:** Screening MRI will occur once all other screening results are available. If a subject is being re-screened (i.e. missed cohort) and there is already a recent MRI scan available within 3 months from their first screening period (ie if subjects were a reserve subject for a previous group but were not dosed and are no longer within the screening window) they do not need to have a repeat MRI scan.
8. **Venous cannulation:** One for administration of [F]-IMA601 (all imaging sessions) and one PK sampling (imaging sessions 2 and 3) (two venous cannulae be used).
9. **[F]-IMA601 Administration:** At the start of each PET scan.

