10. **PET Scan:** Subjects will have one baseline PET scan during imaging session 1, and two on-treatment PET scans during imaging sessions 2 and 3. For session 1, subjects will receive dosing water after a minimum of 10 hours fast (no food or drink except water) and will fast for a further 4 h after their dose with the PET scan done approximately 2 h after taking the dosing water. Other than the dosing water, water is not allowed from 2 h before until 2 h after dosing. The times of on-treatment PET scans for all subsequent groups will be selected based on review of emerging data. Subjects will have no more than 3 PET scans in total during the study.
11. **ASN51 Administration:** Subjects will receive an oral dose of ASN51 following a minimum 10 h fast (no food or drink except water) and will fast for a further 4 h after their dose. Other than the water required to take the study medicine, water is not allowed from 2 h before until 2 h after dosing.
12. **Inpatient Discharge:** Subjects will be inpatient until after their baseline PET in imaging session 1, and until at least 72 h after their dose of study drug in imaging sessions 2 and 3.
13. **Physical Examination:** A full physical and neurological examination will be done at screening visit 1 and at the follow-up visit (or Early Termination visit). All other indicated physical examinations (Day -1 for sessions 2 and 3) should be symptom-directed, and include neurological assessment of cranial nerves, motor, sensation, coordination, reflexes, and gait.
14. **Pregnancy and FSH:** Pregnancy tests in WOCBP only: serum at all timepoints except urine pregnancy test at the MRI visit. FSH at screening only in post-menopausal women. Urine pregnancy test at MRI screening visit to be done at PET site.
15. **Height, Weight, BMI:** BMI and height will be measured at screening visit 1 only.
16. **Vital Signs:** Vital signs consist of systolic and diastolic blood pressure, heart rate, tympanic temperature, and respiratory rate. Assessments will be done at screening, on Day -1 at imaging session 1, pre-dose on Day 1 in imaging sessions 2 and 3, and at follow-up. Single measurements will be made at all time points except screening. At screening, 3 measurements will be made, each 5 minutes apart. Measurements should begin with subjects in a seated position, after they have rested for 5 min. Additional unscheduled assessments may be done at the discretion of the Investigator.

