Subjects will be screened within 21 days before their baseline PET scan. Their on-treatment PET scans will be within 28 days of their baseline scan with an interval of 7–14 days between imaging sessions 2 and 3. Subjects will be confined from Day -1 until about 72 h after drug intake in on-treatment sessions 2 and 3. In session 1, subjects will be confined from day -1 and may leave the clinical unit in the evening of the PET scan on Day 1. In the case of a technical failure (such as unsuccessful tracer synthesis), subjects may be asked to attend an additional on-treatment imaging session, in which they will receive a third oral dose of ASN51. There will be at least 7 days between each dose of ASN51. Subjects will not have more than 3 PET scans or no more than 3 doses of ASN51 during the study.

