### 10.7.2 Assessment and management of risk

#### Risk associated with the imaging techniques

Subjects in this study will be exposed to an additional dose of ionising radiation as a result of their participation. The majority of the radiation dose comes from the administered radioligand, while a smaller portion comes from a low dose computed tomography (CT) scan performed to estimate tissue attenuation. To mitigate this risk, the study will exclude subjects who have had previous exposure to ionising radiation such that, their exposure would be  $> 10\text{mSv}$  for the previous year. A maximum of 100 MBq of [ $^{18}\text{F}$ ]-IMA601 will be injected for each PET scan and the maximal effective dose from ionising radiation for an individual will not exceed 7.4 mSv from the PET and low-dose CT scans. The maximal radiation exposure for each subject over the whole study is presented in Table 2.

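### After a failure that follows tracer injection, the repeat permissions and the caps of 3 no longer fit the planned scans; separately, a permitted repeat with a second CT passes the stated 7.4 mSv maximum

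*Protocol*

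**What the plan says.** **Planned course.** Protocol 7.1: "Each subject will have up to 3 imaging sessions, with one scan in each session". Session 1 is the baseline. Sessions 2 and 3 each have an ASN51 dose and a scan. Tracer is injected as each scan starts.

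**Repeats.** The PET Repeat/Reschedule note to Table 1 counts both failed tracer synthesis and scanner malfunction as technical failures.
- For session 1 it separates failures before and after radioactivity is given. Before, the baseline may be repeated, with no limit stated. After: "If the failure affects imaging session 1 after administration of radioactivity, the baseline scan may be repeated once".
- For sessions 2 and 3 it allows a further session once ASN51 has been taken, and does not ask whether tracer was injected.
- Protocol 7.1, Protocol 10.7.1 and SAP section 5 allow an additional session after a technical failure: "subjects may be asked to attend an additional on-treatment imaging session, in which they will receive a third oral dose of ASN51". Failed synthesis is given as an example, not as a limit.

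**Caps.** The same Table 1 note counts tracer doses: "Subjects will receive no more than 3 single doses of ASN51, or 3 doses of" the tracer. The other statements count scans. Table 1 note 10: "Subjects will have no more than 3 PET scans in total during the study". Protocol 7.1, repeated in SAP section 5: "Subjects will not have more than 3 PET scans or 3 doses of ASN51 during the study". Protocol 10.7.1: "Subjects will not have more than 3 PET scans or no more than 3 doses of ASN51 during the study".

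**Radiation.** Protocol 10.7.2: "the maximal effective dose from ionising radiation for an individual will not exceed 7.4 mSv from the PET and low-dose CT scans". Table 2 builds this figure from exactly three emission scans and three low-dose CT scans.

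**The concern.** The plan has no spare tracer dose, yet it foresees failures that use one up. The permissions for sessions 2 and 3 do not depend on a tracer dose being left, and the repeat baseline comes with no statement that a later session is lost. Read literally, the text schedules or allows an ASN51 session in a healthy volunteer for which no scan remains, and it names no session to drop. Other sections do not settle it: 9.7 defines compliance as all scheduled doses taken, and 7.6.1 lists a missed administration as a possible reason for removal.

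The exposure maximum is a separate matter. It is stated as a ceiling for each individual, and the 10 mSv eligibility limit in exclusion criterion 34 counts this trial's exposure. If a permitted course can pass the ceiling, the figure is not a maximum.

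**Working it through.** **Inputs.** Emission dose per scan: 0.021 mSv/MBq x 100 MBq = 2.1 mSv (Table 2). CT: 0.36 mSv per scan (Table 2 and 9.8). Order: CT first, injection after (10.2). Caps: 3 tracer doses or scans, and 3 ASN51 doses.

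**Step 1: the plan's own figure.** 3 x 2.1 + 3 x 0.36 = 6.30 + 1.08 = 7.38 mSv, rounded to 7.4. It reproduces.

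**Step 2: what the full plan needs after one failure.** The full plan is one valid baseline and two valid on-treatment scans.
- Tracer doses = 3 + number of failures after injection.
- ASN51 doses = 2 + number of failures in session 2 or 3 after ASN51 was taken.
- Exposure = 2.1 x injections + 0.36 x CTs.

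| Single failure | Tracer doses | ASN51 doses | mSv | Fits both caps |
|---|---|---|---|---|
| None | 3 | 2 | 7.38 | yes |
| Session 1, before injection | 3 | 2 | 7.38; 7.74 if CT already done | yes |
| Session 2 or 3, before injection | 3 | 3 | 7.38; 7.74 if CT already done | yes |
| Session 1, after injection | 4 | 2 | 4 x 2.46 = 9.84 | no |
| Session 2 or 3, after injection | 4 | 3 | 4 x 2.46 = 9.84 | no |

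**Step 3: what the caps leave in the rows that do not fit.**
- Session 1: the failed and repeated baselines use 2 tracer doses, so 3 - 2 = 1 remains. Table 1 still schedules ASN51 in sessions 2 and 3.
- Session 2 or 3, both sessions held: baseline, failed session and other session use 3, so 3 - 3 = 0 remain for a session with a third ASN51 dose.

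**Step 4: exposure with every cap obeyed.** A failure after the CT but before injection, then a permitted repeat, gives 3 injections and 4 CTs: 6.30 + 4 x 0.36 = 6.30 + 1.44 = 7.74 mSv. That is 0.34 mSv above 7.4. Two such failures, one at baseline and one in session 2 or 3, still fit 3 tracer and 3 ASN51 doses and give 6.30 + 5 x 0.36 = 8.10 mSv. Both totals are below the 10 mSv guideline cited under Table 2. For eligibility, 10 - 7.4 = 2.6 mSv appears free for earlier research exposure; a subject with 2.6 mSv who then received 7.74 would reach 10.34.

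**The case against.** Two stronger readings are tempting, and the documents support neither.

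- A reader might infer that the third ASN51 dose can never fit the tracer cap. It can. In failed synthesis nothing is injected, so baseline, one good on-treatment scan and the repeat make 3 tracer doses and 3 ASN51 doses. The blood budget in 10.6 points the same way. The 53 mL extra for a repeated session is close to 16 x 2 mL PK + 2 x (2 + 3.5 + 3) mL safety samples + 3.5 mL pregnancy test = 52.5 mL; a further 145 mL of arterial sampling would make it 197.5 mL. That breakdown is an inference, since the 53 mL is not itemised.
- A reader might infer that the protocol allows a fourth injection and 9.84 mSv. It does not. The Table 1 notes, 7.1, 10.7.1 and 10.7.2 all rule it out, and 7.1 sets its cap in the same paragraph as the repeat permission. A fourth injection would be a protocol deviation. The difference in unit between scans and tracer doses does not change this: tracer is given as a scan starts, and a site that counted only completed scans would still be bound by the tracer-dose cap and the exposure ceiling.

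Three more points carry weight. The repeat wording is permissive while the caps are mandatory, and one can argue that an imaging session cannot be held when no scan remains. The Safety Review Committee reviews data before each dose (7.5.1, 7.5.3), which makes dosing without a scan less likely. And the PET population needs only a baseline and one later scan (12.2), so the data loss is one occupancy point in an affected subject.

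What remains is that no text states the condition these arguments supply. After a failure following injection, the documents do not say which session is given up, and dosing without a scan is not excluded in words. None of these points answers the 7.74 mSv result.

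**Conclusion.** The concern holds in a limited form. For a single failure before injection, permissions and caps agree. Once a tracer dose has been lost to a failure after injection, they do not agree with the planned course: the full plan needs 4 tracer doses against a cap of 3, and the text leaves at least one scheduled or permitted ASN51 session without a scan.

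Separately, the 7.4 mSv maximum does not hold for a permitted repeat. One extra CT gives 7.74 mSv, 0.34 mSv over and below 10 mSv. This assumes a failure between CT and injection, a new CT at the repeat, and the maximum activity of 100 MBq at each injection. The documents give no failure rate, so how often either situation would arise cannot be stated.

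The effect on the occupancy analysis is small. The reason to act is that the text governs dosing and radiation in healthy volunteers and can be put right with a few sentences.

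**What to change.** Reconcile the Table 1 notes (PET Repeat/Reschedule and note 10), Protocol 7.1, Protocol 10.7.1 and SAP section 5:
- use one unit for the imaging cap throughout;
- say, separately for failures before and after injection, and for session 1 and for sessions 2 and 3, which sessions remain.

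Reconcile 10.7.2 and Table 2 with the repeat permissions. Either restate the maximum to cover a repeated CT (7.74 mSv for one) or state that repeats are bounded by the 7.4 mSv figure. If the maximum is restated, check that the eligibility budget under exclusion criterion 34 uses the same number.

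Which rule applies is for the sponsor to decide; this point asks only that the passages agree. The cost is wording in a few places, plus either a slightly higher stated exposure or one fewer on-treatment scan in an affected subject.
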